### STUDY PROTOCOL:

Study Design: A single-centre, randomised and counter-balanced, two-arm cross-over study.

**Population:** 32 adults with T1D aged between 18-70 years. Age is restricted to a minimum of 18 years due to the well documented hormonal effects on glycaemic control in adolescents and young adults.

**Inclusion criteria:** A diagnosis of T1D for a minimum of 5 years; Currently treated on a stable insulin regimen for a minimum of 6 months consisting of continuous subcutaneous insulin infusion (CSII) therapy or multiple daily injections (MDI) of a combination of rapid-acting and long-acting insulin; Familiar and currently using the carbohydrate-counting method for determining mealtime insulin dose; Not currently pregnant; No overt diabetes complications including end stage renal failure requiring dialysis; Free from hypoglycaemia unawareness assessed through a combination of the Clarke and Gold methods; No recent (<6-months) history of diabetic ketoacidosis (DKA); Free from medical conditions relating to a haematological disorder, gut mobility or digestion; No history of anorexia, bulimia, or any other disordered eating; No history of deep vein thrombosis; No history of heart attack or stroke within 6 months prior to recruitment; No history of malignancy; No existing medical or psychiatric conditions likely to interfere with the study; No severe functional limitations that contraindicate prolonged episodes of sitting (i.e. back pain) or short frequent bouts of light-intensity walking (i.e. mobility issues); No dietary allergies or intolerances likely to interfere with the study; Able to understand written English and provide written informed consent; Do not currently meet the recommendations for moderate-to-vigorous physical activity (150 min/wk) in adults.

Setting and recruitment strategy: Potential participants will be identified via recruitment using University/charity recruitment materials/websites. Once potential patients have been identified, eligibility checked, and informed consent obtained, participants will be randomised by computer programme to determine the sequence of two cross-over arms. Our team is research active and has significant expertise and experience in recruiting to clinical studies (including those involving CGM) in both T1D and T2D (GLADIS, REPLACE, LIBERATES). Over the 12-month recruitment period of the proposed study, the team will see >1400 individuals with T1D, of which 25-35% are likely to be eligible. Based on our track record, we estimate a participation rate of 20% of those eligible is readily achievable based upon the studies we have previously conducted. Using a conservative estimate, we anticipate recruiting 32 participants (to target) within 6 months, which is, on average 1 participant per week. It should be clear that we have been developing this proposal, and the data to support it, for a long time prior to this call, and collectively have the experience and track-record to ensure successful completion. All reasonable travel expenses will be reimbursed to study participants, and individuals will receive a £100 gift voucher as compensation for their time.

### **Study Protocol:**

**Preliminary visit:** Patients will attend a preliminary visit to our research facility to assess eligibility and obtain written informed consent. At this visit, participants will be fitted with a blinded real-time CGM and an accelerometer and provided with a food diary. During this visit, patients will complete a questionnaire to assess their medical history and physical activity. Both CGM and accelerometer devices will be worn by participants for the duration of their study involvement; both devices complete with data capture will be returned by participants to the research team either in person or via post (using a prepaid envelope).

**CGM measurement:** A small CGM device (CGM; Freestyle Libre Pro; Abbott Diabetes Care) will be inserted during the preliminary visit to the laboratory. It is a small discreet, water resistant sensor, with a thin filament (<0.4m thick) that is inserted (painlessly) 5mm beneath the skin surface on the upper arm. The sensor will be inserted into the subcutaneous tissue on the anterior of the upper arm. The insertion site will be taken as equidistant between the most medial portion of the upper arm and marked with indelible ink so that initial placement can be replicated on subsequent insertions in the unlikely event that a sensor should fail. The sensor is factory calibrated making it far more convenient and removing the risk for sensor inaccuracies from calibration user error (capillary meter inaccuracy, not washing hands etc) seen with other CGM devices. Glucose data generated by the CGM is information). A single reader device is used to activate and retrieve the data. The accuracy and safety of this device has been established in T1D across the full range of glucose levels likely to be observed in this study, including those in the normal range; the latest generation of the CGM sensor has a MARD of <9% as of 2018. Moreover, as an un-blinded version of this device is now made available to people with T1D with treatment indications through the NHS, the use of this technology is deemed acceptable to people with T1D. Study participants who are using Freestyle Libre to monitor their glucose patterns can continue to use the device as usual but will be asked to wear an additional blinded sensor.

Accelerometer: Participants will be issued and fitted with an accelerometer (GeneActiv, worn on the arm) which will provide a comprehensive assessment of sitting/standing patterns (i.e. posture allocated) *and* physical activity levels. The data collected from this device will be used to estimate daily energy expenditure (using a priori cut points) and calculate physical activity levels including time spent in different postures and activities during discrete parts of the day both before and after each laboratory visit. This will allow for quantification, standardisation and replication of physical activity patterns during free-living episodes.

**Medical history**: To include: age, gender, duration of diabetes, insulin therapy (average total daily dose and basal insulin dose), associated medical conditions and family history of T2D and cardiovascular disease. Presence of diabetes complications will be carefully evaluated where possible, including assessment of latest retinal screenings, renal dysfunction (proteinuria or reduced eGFR) and neuropathy (clinical examination), history or symptoms suggestive or coronary artery, and peripheral or cerebrovascular disease.

**Physical activity assessment:** Patients will complete the IPAQ (International Physical Activity Questionnaire), and an Exercise Benefits/Barriers Scale Questionnaire which will assess current levels of physical activity participation, as well as general and diabetes-specific enablers and barriers to physical activity.

Anthropometrics: Anthropometric data will include: weight, height, waist circumference and waist-hip-ratio. Body composition will be determined using the bioelectrical impedance method [Seca mBCA 525] as detailed above. Blood pressure will be taken alongside ankle brachial index measurements. Estimated glucose disposal rate (eGDR; a measure of insulin resistance) will be calculated for all patients.

### **Experimental visits**

**Pre-laboratory phase:** Patients will be required to use their dietary recording sheets to replicate their dietary patterns in the 48-hours prior to each experimental laboratory visit. For standardisation of glycaemic control, as well as biochemical parameters, participants will be provided with a standardised meal to be consumed on the evening before each experimental laboratory visit based upon their weight (~635kcal; vegetarian lasagne; Tesco). Since an acute exercise session may enhance insulin action for up to 48-hours, participants will be asked to reframe from moderate-to-vigorous physical activity/exercise during the 48-hours preceding each laboratory visit, in order to avoid the potential impact of this on glycaemia and hypoglycaemia risk. Additionally, during the 24-hour prior to each laboratory visit, participants will be asked to reframe from caffeine and alcohol which are known to influence glucose levels.

To avoid any confounding influence of hyper/hypoglycaemia or illness, a researcher will call the morning of each testing day – if blood glucose is outside the range of 4-12 mmol/L or if the participant is unwell with blood ketones >0.6 mmol/L, the experimental visit will be postponed. The dosage and timing of insulin administrations as well as any supplements/vitamins being taken will be standardised for the duration of each trial period. To control for the potential confounding effect of insulin regimen (CSII vs MDI) and medication, insulin regimen and medication will be included as a covariate in the statistical model. Participants using CSII will be advised to avoid making changes to their insulin pump delivery settings and insulin regimen between study visits. Participants treated with MDI will be advised not to change their insulin regimen between study visits. Due to the likelihood of changes in glycaemic control and/or insulin requirements over longer periods of time, pre-menopausal women will complete each condition with a 1-week washout, as for all other participants. Menstrual phase will be recorded for each condition and controlled for as a covariate in statistical models.

**Main experimental visits:** In a randomised crossover design, patients will attend two separate morning-time (~08:00am) laboratory-based visits (lasting ~7-hours in duration) within our research facility, each interspersed by one week. Each experimental condition will be conducted in a controlled laboratory setting to maximise internal validity and minimise the inherent variability of less-controlled 'real-world' settings. Except for toilet breaks, participants will be seated in a comfortable lounge-chair and instructed to minimise excessive movement.

On each occasion and upon arrival to the laboratory following an overnight fast, participants will assume a seated and rested position while a 20-guage cannula (Vasofix, B. Braun, Melsungen AG, Melsungen, Germany) is inserted into the antecubital vein of their non-dominant arm; resting, fasted venous blood samples will be collected prior to experimental testing. Following the initial blood sample, patients will be given a standardised mixed-macronutrient breakfast-based meal which will be identical on each occasion. At 3.5-hours post-breakfast, participants will be provided with a standardised mixed-macronutrient lunch meal. Participants will remain in the laboratory under observation for a further 3.5-hours before being discharged home.

Trial sequencing will be randomly assigned with the use of a computerised random-number generator such that participants will perform two experimental conditions (Arm 1 = Sit; Arm 2 = Sit-Less); a schematic of the experimental design is provided in Figure 2.

Arm 1 –Sit (control): Following baseline measurements participants will sit in a lounge chair for 7-hours, with breakfast provided upon beginning the experimental trial (0-hours), and lunch at 3.5-hours (Figure 2).

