### Post-laboratory observation period:

Following the last blood sample at 7-hours post-breakfast, participants will be discharged from the laboratory. Glycaemia will continue to be monitored under free-living conditions for a total of 48-hours post-intervention using CGM. As we are interested in the 48-hour glucose responses following our intervention (including the dawn phenomenon), participants will be given two standardised meals to consume as their evening meal and breakfast, and be required to replicate their dietary intake across trials

for the duration of the 48-hour post-intervention period, in order to control for the potentially confounding effects of diet on glycaemic control. This will provide the unique opportunity to investigate the legacy effects of interrupted sitting on glycaemic parameters, including the dawn phenomenon.

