# Sample size:

Our sample size calculation is based on our preliminary data and primary outcome variable of mean 48-hour interstitial glucose assessed using FDA. Owing to the randomised crossover design of our study, participants will act as their own controls, which enhances both the internal validity and reliability of the data collected and permits a smaller sample size. To detect a significant difference in mean interstitial glucose of 1.6mmol/L with a SD of 1.5 (effect size 0.64) at P <0.05 with 95% power we will require a sample size 32. This is a clinically relevant effect size in people with diabetes; improving CGM glucose by this small, but clinically relevant margin in T1D has been shown to result a reduction of HbA1c by 1.0mmol/mol over the long-term^76. We have shown greater improvements in interstitial glucose in people with T2D in response to interrupted sitting interventions. This number of individuals is enough to detect a 26% difference in clot lysis time with a power of 90% given SD of the variable studied at 22%. This difference in lysis time reflects 18% lower risk of cardiovascular mortality in individuals with acute coronary syndrome, as we demonstrated in our recent study.

Vascular inflammatory, thrombotic and platelet responses: As these are exploratory outcomes with no previous data available on how activity breaks affect platelet biology in T1D it is difficult to provide a formal power calculation. Previously we have infused lipids into healthy subjects and then examined platelet function. In this study we found significant differences in platelet function pre- and post-lipid infusion using 20 healthy participants; as the biochemical abnormality is assumed to be higher in T1D individuals we are confident that our sample size of 32 will be adequate to detect a meaningful difference in our vascular inflammatory, thrombotic and platelet measures.

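### The exercise, alcohol and caffeine restrictions are stated only for the run-up to each visit; most or all of the 48-hour primary glucose window comes afterwards, with a participant instruction on diet but none on activity

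*Protocol*

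**What the plan says.** **Before the visit** (Protocol, Experimental visits, Pre-laboratory phase). Diet is replicated over the preceding 48 hours. On exercise, "participants will be asked to reframe from moderate-to-vigorous physical activity/exercise during the 48-hours preceding each laboratory visit". The reason is given in the same sentence: "Since an acute exercise session may enhance insulin action for up to 48-hours". On drinks, over the last 24 hours, "participants will be asked to reframe from caffeine and alcohol which are known to influence glucose levels".

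**After the visit** (Protocol, Post-laboratory observation period). "Glycaemia will continue to be monitored under free-living conditions for a total of 48-hours post-intervention using CGM". Participants receive two standardised meals, an evening meal and a breakfast, and must "be required to replicate their dietary intake across trials". This applies to the whole 48 hours, and its stated purpose is to limit confounding by diet. The section does not mention physical activity, and it does not name alcohol or caffeine.

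**Primary outcome** (Protocol, Sample size). The calculation is for the "primary outcome variable of mean 48-hour interstitial glucose assessed using FDA". The start of the 48 hours is not given there.

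**Activity data** (Protocol, Accelerometer and Data analysis). The device records activity before and after each visit, and the Accelerometer paragraph says that this makes it possible to quantify, standardise and replicate free-living activity. The Data analysis section then takes diet and activity as replicated across visits and, on that ground, plans no formal statistical analysis of either. The only dietary intake it names for nutritional analysis is that of the 24 hours before the visit.

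**The concern.** The protocol treats exercise, alcohol and caffeine as strong enough influences on glucose to require abstention in the run-up to each visit. The outcome that decides the trial is measured mostly or wholly after the visit, and there the abstention lapses without comment. On the protocol's own statement about how long exercise acts, a single session on the first evening could affect nearly the whole primary window of that condition.

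A crossover protects the paired contrast only if such behaviour is matched between a participant's two windows. Participants cannot be masked to whether they sat for seven hours or took walking breaks, so their behaviour after discharge may depend on the condition. A systematic difference would be bias, which neither randomising the sequence nor a larger sample removes. Unsystematic mismatch would be added within-person noise.

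**Working it through.** **1. How much of the primary window lies after discharge.** The laboratory day lasts 7 hours.
- If the 48 hours start at the end of the visit, as the Post-laboratory section suggests: 48/48 = 100%.
- If they start at breakfast: (48 − 7)/48 = 41/48 = 85%.

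**2. Control in force before and after the visit.**

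| Factor | Before the visit | After the visit |
|---|---|---|
| Diet | Replicated over 48 h; standardised evening meal | Replicated over 48 h; two standardised meals |
| Alcohol, caffeine | Abstention for 24 h | Not named; reasonably within replicated diet |
| Moderate-to-vigorous exercise | Abstention for 48 h | No participant instruction; measured by accelerometer, replication assumed |

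Before the visit, abstention is required on top of dietary replication, so replication alone was not considered enough for drinks. After the visit, only replication remains for drinks, and for activity there is no instruction at all.

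**3. The plan's own sample size.** Inputs from the Sample size section: effect size d = 0.64, P < 0.05, power 95%, n = 32. Two-sided testing is assumed, since sidedness is not stated.
- Normal approximation: n = ((1.960 + 1.645)/0.64)² = 31.7, rounded up to 32. This reproduces the stated figure.
- Exact paired t-test: 34 pairs are needed for 95% power; at n = 32 the power is 93.9% (noncentrality 0.64 × √32 = 3.62).

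**4. Illustration of added noise.** The documents give no figure for the variability that unmatched behaviour would add. Assume that it multiplies the variance of the paired difference by f, so that the effect size becomes d/√f. Power is for the exact paired t-test with n = 32, two-sided 0.05.

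| f (assumed) | 0.64/√f | Power from d = 0.64 | Power from d = 1.6/1.5 = 1.07 |
|---|---|---|---|
| 1.0 | 0.640 | 93.9% | > 99.9% |
| 1.1 | 0.610 | 91.7% | > 99.9% |
| 1.2 | 0.584 | 89.3% | > 99.9% |
| 1.3 | 0.561 | 86.8% | 99.9% |

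The last column is needed because the section's own difference (1.6 mmol/L) and SD (1.5) give 1.07, not the 0.64 printed beside them. The cost in power therefore depends on which figure is meant.

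**5. Bias.** No figure in the documents allows the size of a behavioural difference between conditions to be estimated, so none is offered.

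**The case against.** The strongest reply is that the post-visit window is controlled, by replication instead of abstention. Diet must be matched for the full 48 hours, with the stated purpose of controlling confounding, and alcoholic and caffeinated drinks are reasonably part of dietary intake. An exposure matched in both periods does not bias a paired contrast. Activity is recorded after each visit and the protocol says that it will be replicated. Participants are enrolled only if they fall short of 150 minutes of moderate-to-vigorous activity a week, so a vigorous session is less likely. The window is meant to be free-living, so that legacy effects can be seen. The preliminary data behind the SD may also already contain ordinary behavioural variation, in which case inflating the variance counts it twice.

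Much of this stands. A reader might infer from the lapsed restrictions that the protocol leaves its named confounders uncontrolled in the primary window. The documents do not support that: diet replication covers the whole 48 hours, and activity replication is a declared aim. Nor do they show that power is materially lost, because the inflation is assumed and the loss disappears at 1.6/1.5.

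The part on activity is not answered. The Accelerometer paragraph describes what the data make possible, and the Data analysis section asserts a result. Neither tells participants what to do after discharge, and the section that does set post-visit rules is silent on activity. The eligibility limit reduces exercise but does not exclude it. The free-living argument has limited weight, since diet is already fixed in this window.

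**Conclusion.** The point holds in a limited form. The restrictions on exercise, alcohol and caffeine are stated for the pre-visit period only, while 85% to 100% of the primary window, depending on when it starts, comes after the laboratory day. The gap is clearest for activity, where there is an aim and an assumption but no participant instruction, and where the assumption removes the formal check. It is weaker for alcohol and caffeine, which dietary replication reasonably covers.

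The size is unknown. For noise, power would fall from 93.9% to between 91.7% and 86.8%, given d = 0.64, a two-sided paired t-test and an assumed 10% to 30% increase in the variance of the paired difference; at d = 1.07 it would stay at about 99.9%. The more serious possibility is bias from behaviour that differs by condition in participants who know their condition. The documents do not show that this will happen, but as written the plan neither instructs against it nor formally tests for it. The change is worth making because it is cheap and concerns conduct in the primary window.

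**What to change.** In Post-laboratory observation period, state that the restrictions on moderate-to-vigorous exercise and alcohol continue through the 48-hour observation period of both conditions. State also whether caffeine is restricted or replicated as part of diet. Ask participants to note any breach in the food diary.

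In Data analysis, replace the assumption that activity is replicated with a between-condition comparison of the post-visit accelerometer data, which are already being collected.

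The cost is a few lines in the protocol and participant instructions and one short additional analysis. The downside is two more days of restriction per condition and a slightly less free-living window.

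### Insulin regimen is a covariate for confounding it cannot cause in a within-person comparison; period and pre-visit glucose, which vary within person, are not among the covariates named

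*Protocol*

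**What the plan says.** The design line reads "A single-centre, randomised and counter-balanced, two-arm cross-over study", and the Sample size section relies on the fact that "participants will act as their own controls". The primary outcome there is the "primary outcome variable of mean 48-hour interstitial glucose assessed using FDA".

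The covariates are named under Experimental visits, in the pre-laboratory phase. To deal with possible confounding by pump or injection therapy and by medication, "insulin regimen and medication will be included as a covariate in the statistical model". That paragraph also holds regimen fixed: "Participants treated with MDI will be advised not to change their insulin regimen between study visits", with an equivalent instruction for pump users, and insulin dosage and timing are standardised. A third covariate follows: "Menstrual phase will be recorded for each condition and controlled for as a covariate in statistical models".

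The same section postpones a visit "if blood glucose is outside the range of 4-12 mmol/L" on the test morning, so any starting value within that range is accepted at either visit. The Laboratory meals paragraph says that meal boluses carry no correction dose. The blinded CGM is fitted at the preliminary visit and worn throughout. The Data analysis section lists CGM summaries and functional data analysis but sets out no model, and the protocol names neither period nor starting glucose as a model term.

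**The concern.** In a two-period crossover, a variable can confound the condition effect only if it differs between a participant's two visits. Regimen is fixed by the protocol's own instructions, so the stated reason for adjusting does not apply. The protocol thus claims a protection that the design already gives and that the model term cannot add.

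Visit order and glucose at the start of each visit do differ within a person. The accepted morning range is 8 mmol/L wide (12 − 4), and with no correction dose at meals a starting difference may carry into the outcome. If neither is in the model, their contribution stays in the error of the primary comparison. At stake is precision in a 32-person trial.

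**Working it through.** **1. What cancels.** For participant i at visit j, let the outcome be μ + τ·condition + π·period + β·regimen(i) + γ·baseline(ij) + person effect(i) + error(ij). Take Sit-Less minus Sit within the participant:

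D(i) = τ ± π + γ·[baseline(Sit-Less) − baseline(Sit)] + error difference.

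The terms β·regimen and person effect are the same at both visits and drop out. The period term (its sign set by sequence) and the baseline difference remain. Medication behaves like regimen only if it too is unchanged; the protocol standardises insulin dosing and supplements but says less about other drugs.

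**2. Numerical check of the cancellation.** In 20 simulated 32-person crossovers with complete data, mixed models with a random participant intercept were fitted with and without regimen and medication main effects. Regimen was given a true effect of 1.5 mmol/L and medication 1.0 mmol/L on the participant's level. The largest change in the condition estimate was 4 × 10⁻¹⁵ mmol/L, and in its standard error 6 × 10⁻⁶.

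**3. The plan's own figure.** Inputs from Sample size: effect size 0.64, P < 0.05 (taken as two-sided), 95% power. Paired formula: n = [(1.960 + 1.645)/0.64]² = 31.7, so 32, as stated. Power at n = 32 is 95.2% by the normal approximation and 93.9% by the noncentral t with 31 df. The t figure is the reference below.

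The printed 1.6 mmol/L and SD 1.5 give 1.6/1.5 = 1.07, not 0.64. An effect size of 0.64 with a difference of 1.6 implies an SD of differences of 1.6/0.64 = 2.5, which is used here because it is the reading that yields 32.

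**4. Adding period and the baseline difference.** Let r be the correlation between the baseline difference and the outcome difference. The documents do not give it, so it is assumed. Residual variance is multiplied by 1 − r², the effect size becomes 0.64/√(1 − r²), and 29 df remain.

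| r (assumed) | 1 − r² | effect size | power | equivalent n = 32/(1 − r²) |
|---|---|---|---|---|
| 0 | 1.00 | 0.640 | 93.8% | 32 |
| 0.2 | 0.96 | 0.653 | 94.6% | 33.3 |
| 0.3 | 0.91 | 0.671 | 95.6% | 35.2 |
| 0.5 | 0.75 | 0.739 | 98.1% | 42.7 |

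**5. Leaving period out.** With equal sequences, an unmodelled period effect π spreads the differences, so the SD becomes √(2.5² + π²). The size of π is assumed.

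- π = 0.5: √6.50 = 2.550; 1.6/2.550 = 0.628; power 93.0%.
- π = 1.0: √7.25 = 2.693; 1.6/2.693 = 0.594; power 90.2%.
- Period in the model, 30 df: power 93.8% whatever π is.

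This formula is slightly pessimistic under exact balance, where π inflates the estimated SD but not the true variance of the mean difference. Simulating 400,000 trials at 16:16 with SD 2.5 gave 93.4% and 91.7% for the two values.

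**6. Sensitivity to the SD.** If the SD of differences were the printed 1.5 with a difference of 1.6, power would exceed 99.9% without adjustment, and would be 99.98% and 99.8% with period effects of 0.5 and 1.0 ignored. The gains in steps 4 and 5 would then not matter for power, though intervals would still narrow.

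**The case against.** The strongest reply is that the regimen covariate does no harm and that model terms are commonly left to a statistical analysis plan, which may exist but is not shown. Naming some covariates does not exclude others. That stands in part: the absence of period and baseline would not be a finding by itself. But the protocol does choose covariates and gives a reason for them, and that reason is wrong for this design.

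The evening meal, the 48-hour diet, activity, caffeine and alcohol are also controlled before each visit, so actual differences in starting glucose may be much smaller than the accepted range allows. That is fair, and it is why r is shown as a range that includes zero.

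The cancellation is exact only for main effects with both visits observed. With a missing visit, a mixed model recovers some between-person information and regimen can then matter slightly.

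A reader might go further in four ways that the protocol does not support.

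- That omitting period biases the result. It does so only if the sequences are unequal; at 16:16 the cost is precision alone.
- That sequences will be unequal because "Trial sequencing will be randomly assigned with the use of a computerised random-number generator". A balanced or blocked list is also made with random numbers, the design line promises counter-balancing, and simple randomisation is stated nowhere.
- That the menstrual-phase covariate would discard most participants. No sex or menopausal mix is given and no deletion of participants without a phase is planned. Phase is recorded per visit, so it can vary within a person and is a reasonable covariate; only its coding is unstated.
- That the functional data analysis should be displaced. Nothing here requires that.

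**Conclusion.** The point holds as a correctable weakness in the choice and justification of covariates, not as an error that invalidates the comparison. Adjusting for regimen as a main effect neither removes confounding nor improves precision when both visits are complete.

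The benefit of the better choice is modest: from 93.9% to about 95.6–98.1% power through the baseline, and avoidance of a fall to about 93.0–90.2% if a period effect exists. These figures rest on n = 32, a two-sided 5% level, an SD of differences of 2.5, and assumed values of 0.3–0.5 for the correlation and 0.5–1.0 mmol/L for the period effect. None of the assumed values comes from the protocol. The cancellation itself needs only complete pairs and an unchanged regimen.

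**What to change.** - In the pre-laboratory phase text, remove the statement that the regimen covariate controls confounding. Say instead that regimen is held constant by design, and state whether other medication is too.
- Name period and visit-specific baseline glucose as terms in the primary within-person model for mean 48-hour glucose. Define the baseline as mean blinded CGM glucose over a fixed window before each visit (for example 24 or 48 hours), entered as the within-person difference. Visits a week apart leave room for this window after the first visit's 48-hour follow-up. CGM is the safer source because venous glucose is not among the assays listed under Blood sampling.
- Keep the functional data analysis as planned.
- Use regimen only in a pre-specified condition-by-regimen interaction, labelled exploratory.
- As a wording point, give menstrual phase a 'not applicable' level for participants without one.

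The cost is a few sentences and about two degrees of freedom (31 to 29) for period and baseline, with no new measurements. If the baseline correlation is near zero there is no gain, and power moves from 93.9% to 93.8%. The choice should be fixed before outcome data are compared by condition.
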